## **4. MATERIALS AND METHODS**

### **4.1 PATIENTS**

Approximately 730 patients with mCRPC who have failed an androgen synthesis inhibitor (e.g., abiraterone) and have failed, are ineligible for, or refused a taxane regimen will be enrolled in this study.

#### 4.1.1 **Inclusion Criteria**

Patients must meet the following criteria for study entry:

- Signed Informed Consent Form
- Age  $\geq$  18 years
- Ability to comply with the study protocol, in the investigator's judgment
- ECOG performance status of 0 or 1
- Life expectancy  $\geq$  3 months
- Histologically confirmed adenocarcinoma of the prostate
  - Disease must be either metastatic or locally confined inoperable disease that cannot be treated with definitive intent (no chance for a curative intervention)
  - Patients presenting with treatment emergent neuroendocrine differentiation, but not primary small cell features, are eligible
- Known castrate-resistant disease, defined as meeting all of the following criteria:
  - Castrate serum testosterone level  $\leq$  50 ng/dL (1.7 nmol/L) at the screening visit
  - Bilateral orchiectomy or maintenance on androgen ablation therapy with luteinizing hormone-releasing hormone agonist or antagonist or polyestradiol phosphate for the duration of the study (including the follow-up period)
- Progressive disease prior to screening by PSA or imaging per PCWG3 criteria during or following the direct prior line of therapy in the setting of medical or surgical castration. Disease progression for study entry is defined as one or more of the following three criteria:
  - PSA progression defined as two increases in PSA over a previous reference value of  $\geq$  1 ng/mL ( $\mu$ g/L) as the minimum starting value (i.e., a minimum of 3 PSA values total), with each progression measurement at least 1 week apart
  - Soft tissue disease progression defined by RECIST v1.1
    - Previously normal ( $<$  1.0 cm) lymph nodes must have grown by  $\geq$  5 mm in the short axis to be considered to have progressed
  - Bone disease progression defined by two or more new lesions on bone scan
- One prior regimen/line of a taxane-containing regimen for mCRPC or refusal or ineligibility of a taxane-containing regimen
  - Patients who have received a taxane-containing regimen for metastatic HSPC are eligible.
  - Patients who refuse or are ineligible for a taxane-containing regimen are eligible for enrollment if they have no intention to use cytotoxic chemotherapy within the next 6 months after an informed discussion.
  - A taxane-containing treatment should be considered in patients with symptomatic and extensive visceral disease who have not previously received and are good candidates for a taxane-containing regimen.

- Progression on a prior regimen/line of an androgen synthesis inhibitor for prostate cancer (e.g., abiraterone, orteronel or galeterone)
  - Patients must have received at least 28 days of an androgen synthesis inhibitor.
  - Prior treatment with first generation antiandrogens (e.g., nilutamide, bicalutamide), oral ketoconazole, vaccines (e.g., sipuleucel-T, prostrvac VF), and radium-223 dichloride is also allowed in addition to one prior regimen or line of an androgen synthesis inhibitor for prostate cancer.
- Patients receiving bisphosphonate or denosumab therapy must have been on a stable dose for at least 4 weeks.
- Availability of a representative tumor specimen from a site not previously irradiated that is suitable for determination of PD-L1 status via central testing
  - A formalin-fixed, paraffin-embedded (FFPE) tumor specimen in a paraffin block (preferred) or at least 15 slides containing unstained, freshly cut, serial sections must be submitted along with an associated pathology report prior to study enrollment. If only 10–14 slides are available, the patient may still be eligible for the study, after discussion with and approval by the Medical Monitor. If archival tumor tissue is unavailable or is determined to be unsuitable for required testing, tumor tissue must be obtained from a biopsy performed at screening. No tissue will be collected for patients enrolled in the safety run-in phase. Refer to Section 4.5.6 for additional information on tumor specimens collected at screening. Tissue from bone metastases might be acceptable after consultation with the Medical Monitor.
- Adequate hematologic and end-organ function, defined by the following laboratory test results, obtained within 14 days prior to initiation of study treatment:
  - ANC  $\geq 1.5 \times 10^9/L$  (without granulocyte colony-stimulating factor support within 2 weeks prior to Cycle 1, Day 1)
  - Lymphocyte count  $\geq 0.5 \times 10^9/L$
  - Platelet count  $\geq 100 \times 10^9/L$  without transfusion
  - Hemoglobin  $\geq 9$  g/dL

Patients may be transfused or receive erythropoietic treatment to meet this criterion

  - AST and ALT  $\leq 2.5 \times ULN$ , with the following exception:
    - Patients with documented liver metastases: AST and ALT  $\leq 5 \times ULN$
  - Serum bilirubin  $\leq 1.5 \times ULN$  with the following exception:
    - Patients with known Gilbert disease: serum bilirubin level  $\leq 3 \times ULN$
  - Creatinine clearance  $\geq 30$  mL/min (calculated using the Cockcroft-Gault formula)
  - Serum albumin  $\geq 2.5$  g/dL
  - For patients not receiving therapeutic anticoagulation: INR or aPTT  $\leq 1.5 \times ULN$  within 14 days prior to initiation of study treatment
- For patients receiving therapeutic anticoagulation: stable anticoagulant regimen

- For men who are not surgically sterile: agreement to remain abstinent (refrain from heterosexual intercourse) or use contraceptive measures, and agreement to refrain from donating sperm, as defined below:

With female partners of childbearing potential, men must remain abstinent or use a condom plus an additional contraceptive method that together result in a failure rate of < 1% per year during the treatment period and for at least 3 months after the last dose of enzalutamide. Men must refrain from donating sperm during this same period.

With pregnant female partners, men must remain abstinent or use a condom during the treatment period and for 3 months after the last dose of enzalutamide to avoid exposing the embryo.

The reliability of sexual abstinence should be evaluated in relation to the duration of the clinical study and the preferred and usual lifestyle of the patient. Periodic abstinence (e.g., calendar, ovulation, symptothermal, or postovulation methods) and withdrawal are not acceptable methods of contraception.

#### **4.1.2 Exclusion Criteria**

Patients who meet any of the following criteria will be excluded from study entry:

##### Cancer-specific exclusions

- Prior treatment with enzalutamide or any other newer hormonal androgen receptor inhibitor (e.g., apalutamide, ODM-201)
- Treatment with any approved anti-cancer therapy, including chemotherapy, immunotherapy, radiopharmaceutical or hormonal therapy (with the exception of abiraterone), within 4 weeks prior to initiation of study treatment
  - Palliative radiotherapy for bone metastases or soft tissue lesions should be completed >7 days prior to baseline imaging.
  - ADT with a gonadotropin-releasing hormone (GnRH) analog (GnRH agonist or GnRH antagonist) is allowed.
- Treatment with abiraterone within 2 weeks prior to study treatment
- Use of herbal products that may have hormonal anti-prostate cancer activity and/or are known to decrease PSA levels (e.g., saw palmetto) within 4 weeks of enrollment
- Treatment with any other investigational agent or participation in another clinical study with therapeutic intent within 4 weeks prior to initiation of study treatment
- Planned palliative procedures for alleviation of bone pain such as radiation therapy (unless completed >7 days prior to baseline imaging) and surgery.
  - Symptomatic lesions amenable to palliative radiotherapy (e.g., bone metastases or metastases causing nerve impingement) should be treated prior to initiation of study treatment.
- Structurally unstable bone lesions suggesting impending fracture

- Uncontrolled pleural effusion, pericardial effusion, or ascites requiring recurrent drainage procedures (once monthly or more frequently)
  - Patients with indwelling catheters (e.g., PleurX®) are allowed.
- Uncontrolled hypercalcemia defined as one or more of the following criteria:
  - Ionized calcium > 1.5 mmol/L
  - Serum calcium > 12 mg/dL
  - Corrected serum calcium greater than ULN (if serum albumin < 4.0 g/dL)
- Known or suspected brain metastasis or active leptomeningeal disease
- Patients with treated epidural lesions and no other epidural progression are allowed.
  - Asymptomatic metastatic lesions whose further growth would likely cause functional deficits or intractable pain (e.g., epidural metastasis that is not presently associated with spinal cord compression) should be considered for loco-regional therapy if appropriate prior to initiation of study treatment.

#### General medical exclusions

- Malignancies other than mCRPC within 5 years prior to initiation of study treatment
  - Patients with malignancies of a negligible risk of metastasis or death (e.g., risk of metastasis or death < 5% at 5 years) are eligible provided they meet all of the following criteria:
    - Malignancy treated with expected curative intent (e.g., adequately treated basal or squamous cell skin cancer)
    - No evidence of recurrence or metastasis by follow-up imaging and any disease-specific tumor markers
- Significant cardiovascular disease, such as New York Heart Association cardiac disease (Class II or greater), myocardial infarction or cerebrovascular accident within 3 months prior to enrollment, unstable arrhythmia, or unstable angina
  - Patients with a known left ventricular ejection fraction (LVEF) < 40% will be excluded.
  - Patients with known coronary artery disease, congestive heart failure not meeting the above criteria, or LVEF 40%–50% must be on a stable medical regimen that is optimized in the opinion of the treating physician, in consultation with a cardiologist if appropriate. Patients with a history of clinically significant cardiac disease (including anatomic abnormality, coronary artery disease, congestive heart failure, abnormal LVEF, arrhythmia, or abnormal ECG) will be required to undergo a screening echocardiogram.
  - History of clinically significant ventricular dysrhythmias (e.g., ventricular tachycardia, ventricular fibrillation, torsades de pointes)
  - History of a Mobitz II second degree or third degree heart block without permanent pacemaker in place

Hypotension (systolic blood pressure < 86 mmHg) or bradycardia with a heart rate < 50 beats per minute at the screening visit

Uncontrolled hypertension as indicated by a resting systolic blood pressure > 170 mm Hg or diastolic blood pressure > 105 mm Hg at the screening visit

- Major surgical procedure other than for diagnosis within 4 weeks prior to initiation of study treatment or anticipation of need for a major surgical procedure during the course of the study
- Any other disease, metabolic dysfunction, physical examination finding, or clinical laboratory finding that contraindicates the use of an investigational drug, may affect the interpretation of the results, or may render the patient at high risk from treatment complications

#### Exclusion criteria related to atezolizumab

- History of severe allergic, anaphylactic, or other hypersensitivity reactions to chimeric or humanized antibodies or fusion proteins
- Known hypersensitivity to biopharmaceuticals produced in Chinese hamster ovary cells or any component of the atezolizumab formulation
- Active or history of autoimmune disease or immune deficiency, including, but not limited to, myasthenia gravis, myositis, autoimmune hepatitis, systemic lupus erythematosus, rheumatoid arthritis, inflammatory bowel disease, antiphospholipid antibody syndrome, Wegener granulomatosis, Sjögren's syndrome, Guillain-Barré syndrome, or multiple sclerosis (see [Appendix 10](#) for a more comprehensive list of autoimmune diseases and immune deficiencies), with the following exceptions:

Patients with a history of autoimmune-related hypothyroidism who are on thyroid-replacement hormone are eligible for the study.

Patients with controlled Type 1 diabetes mellitus who are on an insulin regimen are eligible for the study.

Patients with eczema, psoriasis, lichen simplex chronicus, or vitiligo with dermatologic manifestations only (e.g., patients with psoriatic arthritis are excluded) are eligible for the study provided all of following conditions are met:

Rash must cover < 10% of body surface area

Disease is well controlled at baseline and requires only low-potency topical corticosteroids

No occurrence of acute exacerbations of the underlying condition requiring psoralen plus ultraviolet A radiation, methotrexate, retinoids, biologic agents, oral calcineurin inhibitors, or high-potency or oral corticosteroids within the previous 12 months

- Prior allogeneic stem cell or solid organ transplantation

- History of idiopathic pulmonary fibrosis, organizing pneumonia (e.g., bronchiolitis obliterans), drug-induced pneumonitis, or idiopathic pneumonitis, or evidence of active pneumonitis on screening chest computed tomography (CT) scan
  - History of radiation pneumonitis in the radiation field (fibrosis) is permitted.
- Positive HIV test at screening
- Active hepatitis B virus (HBV) infection (chronic or acute), defined as having a positive hepatitis B surface antigen (HBsAg) test at screening
  - Patients with a past or resolved HBV infection, defined as having a negative HBsAg test and a positive total hepatitis B core antibody (HBcAb) test at screening, are eligible for the study.
- Active hepatitis C virus (HCV) infection, defined as having a positive HCV antibody test followed by a positive HCV RNA test at screening
  - The HCV RNA test will be performed only for patients who have a positive HCV antibody test.
- Active tuberculosis
- Severe infection within 4 weeks prior to initiation of study treatment including, but not limited to, hospitalization for complications of infection, bacteremia, or severe pneumonia
- Treatment with therapeutic oral or IV antibiotics within 2 weeks prior to initiation of study treatment
  - Patients receiving prophylactic antibiotics (e.g., to prevent a urinary tract infection or chronic obstructive pulmonary disease exacerbation) are eligible for the study.
- Treatment with a live, attenuated vaccine within 4 weeks prior to initiation of study treatment or anticipation of need for such a vaccine during the course of the study
- Prior treatment with CD137 agonists or immune checkpoint blockade therapies, including anti-CTLA-4, anti-PD-1, and anti-PD-L1 therapeutic antibodies
- Treatment with systemic immunostimulatory agents (including, but not limited to, interferon and interleukin 2) within 4 weeks or five half-lives of the drug, whichever is shorter, prior to initiation of study treatment
- Treatment with systemic immunosuppressive medication (including, but not limited to, corticosteroids, cyclophosphamide, azathioprine, methotrexate, thalidomide, and anti-tumor necrosis factor [TNF]- $\alpha$  agents) within 2 weeks prior to initiation of study treatment or anticipation of need for systemic immunosuppressive medication during the course of the study, with the following exceptions:
  - Patients who received acute, low-dose, systemic immunosuppressant medication or a one-time pulse dose of systemic immunosuppressant medication (e.g., 48 hours of corticosteroids for a contrast allergy) are eligible for the study.

Patients who received mineralocorticoids (e.g., fludrocortisone), corticosteroids for chronic obstructive pulmonary disease (COPD) or asthma, or low-dose corticosteroids for orthostatic hypotension or adrenal insufficiency are eligible for the study.

The use of systemic corticosteroids of no greater than the equivalent of 10 mg of prednisone or prednisolone per day for symptomatic treatment of prostate cancer is allowed if the patient has been on a stable dose within 2 weeks prior to initiation of study treatment. There should be no plans to taper the patient off treatment or increase the dose during the study.

Patients who are tapered off systemic corticosteroids as part of a prior anti-cancer regimen must have received the last dose  $\geq 7$  days prior to initiation of study treatment.

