#### **4.4.4 Prohibited Therapy**

Use of the following concomitant therapies is prohibited as described below:

- Concomitant therapy intended for the treatment of cancer whether health authority-approved or experimental, is prohibited for various time periods prior to starting study treatment, depending on the agent (see Section 4.1.2), and during study treatment until disease progression is documented and the patient has discontinued study treatment, except as outlined in Section 4.4.1.

Therapy intended for the treatment of cancer may include, but is not limited to, chemotherapy, hormonal therapy (other than protocol required treatment with GnRH analog or GnRH antagonist), immunotherapy, radiotherapy including radium-223 dichloride, and herbal therapy

- Investigational therapy (other than protocol-mandated study treatment) is prohibited within 4 weeks prior to initiation of study treatment and during study treatment.
- Live, attenuated vaccines (e.g., FluMist®) are prohibited within 4 weeks prior to initiation of study treatment, during treatment with atezolizumab, and for 5 months after the last dose of atezolizumab.

- Systemic immunostimulatory agents (including, but not limited to, interferons and IL-2) are prohibited within 4 weeks or five half-lives of the drug, whichever is longer, prior to initiation of study treatment and during study treatment because these agents could potentially increase the risk for autoimmune conditions when given in combination with atezolizumab.
- Systemic immunosuppressive medications (including, but not limited to, cyclophosphamide, azathioprine, methotrexate, and thalidomide) are prohibited during study treatment because these agents could potentially alter the efficacy and safety of atezolizumab.

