### **4.5.1 Informed Consent Forms and Screening Log**

Written informed consent for participation in the study must be obtained before performing any study-related procedures (including screening evaluations). Informed Consent Forms for enrolled patients and for patients who are not subsequently enrolled will be maintained at the study site.

All screening evaluations must be completed and reviewed to confirm that patients meet all eligibility criteria before enrollment. The investigator will maintain a screening log to record details of all patients screened and to confirm eligibility or record reasons for screening failure, as applicable.

Patients who show apparent radiographic progression at a tumor response evaluation must sign a consent form at that time to acknowledge deferring other treatment options in favor of continuing study treatment.

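### The pre-treatment washout for systemic immunostimulatory agents is the shorter of two limits in the eligibility criteria but the longer of the same two limits under prohibited therapy (minor)

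*Combined protocol and SAP*

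**What the plan says.** The exclusion criteria related to atezolizumab appear twice, in the synopsis and in Section 4.1.2. Both exclude a patient treated with systemic immunostimulatory agents (interferon and interleukin 2 are the named examples) "within 4 weeks or five half-lives of the drug, whichever is shorter, prior to initiation of study treatment".

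Section 4.4.4 (Prohibited Therapy) covers the same class. There the agents "are prohibited within 4 weeks or five half-lives of the drug, whichever is longer, prior to initiation of study treatment", and also during study treatment. It gives a safety reason: "because these agents could potentially increase the risk for autoimmune conditions when given in combination with atezolizumab".

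Enrollment is decided on the eligibility list. Section 4.5.1 states: "All screening evaluations must be completed and reviewed to confirm that patients meet all eligibility criteria before enrollment". No section says which of the two intervals takes precedence.

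**The concern.** The class, the two limits and the anchor (start of study treatment) are the same; only the choice between the limits is reversed. A site that checks a candidate against Section 4.1.2, as Section 4.5.1 requires, can correctly find him eligible and then give a first dose inside the Section 4.4.4 window.

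The restriction exists because of a possible added autoimmune risk with atezolizumab, and the list that controls entry carries the less protective interval. What is at stake is the safety margin for the patients concerned and a clear rule for sites. The efficacy analysis is not at stake.

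**Working it through.** The plan states no figure to reproduce here. The check sets the texts side by side and does one line of arithmetic.

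**1. The texts compared**

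| Source | Agents | Limits | Rule | Anchor |
|---|---|---|---|---|
| Synopsis, exclusion criteria related to atezolizumab | Systemic immunostimulatory | 4 weeks; five half-lives | Shorter | Start of study treatment |
| Section 4.1.2, same heading | Same | Same | Shorter | Same |
| Section 4.4.4 | Same | Same | Longer | Same |

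**2. Size of the gap.** Let t be the half-life in days.

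- Section 4.1.2 window = min(28, 5t)
- Section 4.4.4 window = max(28, 5t)
- Gap = max(28, 5t) − min(28, 5t) = |28 − 5t|
- The gap is zero only if 5t = 28, that is t = 5.6 days.

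The documents give no half-life for any of these agents, so the values of t below are assumptions that show the range for short half-lives:

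| Assumed t | Section 4.1.2 window (days) | Section 4.4.4 window (days) | Gap (days) |
|---|---|---|---|
| 8 hours (1/3 day) | 1.7 | 28 | 26.3 |
| 1 day | 5 | 28 | 23 |
| 2 days | 10 | 28 | 18 |
| 5.6 days | 28 | 28 | 0 |

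Above 5.6 days the gap is 5t − 28. The documents identify no agent with such a half-life, so I attach no figure to that case.

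**3. What other exclusions close.** Two cancer-specific exclusions in Section 4.1.2 set a flat 4 weeks whatever the half-life: "Treatment with any approved anti-cancer therapy, including chemotherapy, immunotherapy, radiopharmaceutical or hormonal therapy (with the exception of abiraterone), within 4 weeks", and "Treatment with any other investigational agent or participation in another clinical study with therapeutic intent within 4 weeks prior to initiation of study treatment". For anti-cancer or investigational use with t ≤ 5.6 days, the operative window is therefore 28 days under both sections, and the gap is 28 − 28 = 0.

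Section 4.1.2 narrows the field further by excluding:

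- "Malignancies other than mCRPC within 5 years prior to initiation of study treatment", with an exception for malignancies of negligible risk;
- autoimmune disease or immune deficiency, with listed exceptions;
- a positive HIV test, active hepatitis B and active hepatitis C;
- severe infection within 4 weeks;
- any prior CD137 agonist or checkpoint inhibitor.

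**4. What remains open.** A patient can pass Section 4.1.2 and breach Section 4.4.4 in only two situations:

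- an agent with t < 5.6 days, given neither as anti-cancer therapy nor as an investigational product, and last taken between 5t and 28 days before treatment;
- an agent with t > 5.6 days, last taken between 28 and 5t days before treatment.

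**5. Which version fits the rest of the protocol.** The pre-treatment intervals for live vaccines and for investigational therapy are 4 weeks in both sections. The only other washout expressed in half-lives, for the enzalutamide PK cohort, takes the longer limit. This is consistent with a drafting slip in the eligibility lists but does not prove one.

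**The case against.** The strongest reply is that the two rules can both be obeyed. A site that keeps the longer interval meets both, so the longer one binds in practice, and a site caught out has read Section 4.1.2 but overlooked Section 4.4.4. That is true, and it is why the point is minor. It does not remove the conflict, because entry is confirmed against the eligibility criteria and those state the shorter interval.

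A second reply is that Section 4.4 defines concomitant therapy as starting 7 days before treatment, which might confine Section 4.4.4 to that week. On that reading the gap would survive only for t below 7/5 = 1.4 days, with width 7 − 5t: 5.3 days at 8 hours and 2 days at 1 day. But the bullets in Section 4.4.4 state their own pre-treatment windows of 4 weeks or more, so the 7-day definition cannot be what limits them.

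A third reply is that Section 4.4.4 defers to Section 4.1.2. Only its first bullet does, for therapy intended to treat cancer, which "is prohibited for various time periods prior to starting study treatment, depending on the agent (see Section 4.1.2"). The immunostimulatory bullet has no such reference and sets its own interval.

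It is fair to say that the documents cannot settle which word was intended. Choosing the longer interval is a conservative choice, supported by the stated safety reason.

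A reader might also infer that patients admitted under the shorter interval were ineligible, or that their deviation status is open. The documents do not support this. A patient who meets Section 4.1.2 as written is not an eligibility deviation; at most he breaches Section 4.4.4. Section 6.2 summarizes only major deviations, and nothing shows that such a case would count as major.

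**Conclusion.** Wrong as written; minor. The current text contains two incompatible washouts for one class of agents, and the less protective one sits in the list that decides enrollment.

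The number of patients affected is not given. That it is very small, out of about 730 planned, is a judgement based on the overlapping exclusions, and no affected patient can be identified from the documents. The gap widths rest on assumed half-lives; the existence of the gap for any half-life other than 5.6 days does not.

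Nothing here touches the overall survival analysis, power or type I error, and it would be wrong to read the inconsistency as casting doubt on the trial's result. Sections 3.3 and the synopsis state that the study is being closed for futility, so the prospective effect is small and may be nil.

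**What to change.** Replace the shorter limit with the longer one in the synopsis and in Section 4.1.2. A patient who meets the longer interval satisfies both sections, and the wording then agrees with the autoimmune-risk reason in Section 4.4.4.

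If no further amendment is planned, a note to file stating that the longer interval governs is sufficient. The note should add that any case already recorded is a prohibited-therapy deviation under Section 4.4.4 only, and that patients enrolled under Section 4.1.2 as written are not to be reclassified as eligibility deviations.

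The cost is one word in two places, or one note. The downside is a longer wait at screening for a few patients, if any are still being screened: up to about 26 days at an assumed 8-hour half-life. Sample size and analysis are unchanged.
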